13 STATISTICAL ANALYSIS

This trial is designed to allow preliminary assessments of safety/tolerability and efficacy of belimumab in the post-allogeneic stem cell transplant setting. No pre-specified hypothesis testing will be performed. All analyses of demographics, biological activity, and safety will be descriptive. A 90% exact binomial confidence interval will be constructed for preliminary efficacy information. Data obtained from correlative studies will be used to identify parameters associated with efficacy from belimumab treatment that will guide design of subsequent larger clinical trials. Age-, disease-, and donor-matched subjects will be used as an institutional control. These control subjects will be identified within the Bone Marrow Transplant and Lymphoma Tissue Bank (HRPO# 201103349). Presently, there are roughly 100 subjects with banked specimens and associated clinical outcomes data that will serve as the comparator in this study in assessing preliminary efficacy. The data from this study will be used for sample size calculation estimates of an expansion cohort in a subsequent phase II study. A total of N=10 patients will be enrolled for this study. Though the sample size was not determined based on statistical power, this would provide us reasonable precision on both safety and feasibility. Based on intensive simulation studies regarding the sample size for pilot and translational studies, Piantadosi (2005) recommends that a sample size of 10 to 20 patients be adequate to provide preliminary information. For safety assessment, for example, there would be 90% chance of observing at least 1 serious adverse event if the true rate is at least 20%. Conversely, there would be less than 10% chance that we would observe 2 or more serious adverse events if the true rate is less than 5%.

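### The two probabilities supporting N=10 on safety use different SAE cut-offs and suggest more discrimination than any one count gives; the primary safety endpoint has no planned interval

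*Combined protocol and SAP*

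**What the plan says.** Section 13 fixes the size of the study ("A total of N=10 patients will be enrolled for this study") and is open that power was not the basis: "Though the sample size was not determined based on statistical power, this would provide us reasonable precision on both safety and feasibility". It cites a general recommendation of 10 to 20 patients for preliminary information, and then gives two safety examples.

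- High rate: "there would be 90% chance of observing at least 1 serious adverse event if the true rate is at least 20" percent.
- Low rate, introduced as the converse, with a bound of 5%: "Conversely, there would be less than 10% chance that we would observe 2 or more serious adverse events if the true rate is less than" that.

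On analysis, Section 13 says "No pre-specified hypothesis testing will be performed" and that safety will be described. The only interval it plans is for another purpose: "A 90% exact binomial confidence interval will be constructed for preliminary efficacy information". Sections 2.1, 5 and 8.1 make safety and tolerability the primary endpoint, evaluated in every subject who receives any study treatment. No section names an acceptable or unacceptable number of SAEs. The numerical safety trigger is in Section 5.10, where a single death at least possibly related to treatment suspends the study.

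**The concern.** The two examples are joined as if they were the two sides of one reading of the SAE count: likely to show a signal when the rate is high, unlikely to show one when it is low. They do not describe the same count. The first asks whether any SAE is seen, the second whether two or more are seen. A reader who takes them as a pair would think that 10 subjects separate a 5% rate from a 20% rate with about a 10% error each way.

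This matters because the examples are the only quantitative support given for precision on safety. The primary endpoint also comes with no measure of uncertainty of its own, so a report following Section 13 could give a low SAE count without showing what rates remain compatible with it. Section 13 says the data will feed the sample size of a later phase II study, and its planners would need that information.

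**Working it through.** **Inputs.** n = 10 and the true rates of 20% and 5% come from Section 13, as do the two cut-offs (at least 1; 2 or more). X is the number of subjects with at least one SAE, taken as binomial with independent subjects. That definition of the SAE rate is an assumption, because Section 13 does not say whether it counts subjects or events. All 10 enrolled subjects are assumed treated.

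**Step 1: reproduce the plan's figures.**

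- P(X ≥ 1 | p = 0.20) = 1 − 0.8^10 = 1 − 0.10737 = 0.8926. The plan gives 90%; an exact 90% needs p = 1 − 0.1^(1/10) = 0.2057.
- P(X ≥ 2 | p = 0.05) = 1 − 0.95^10 − 10(0.05)(0.95^9) = 1 − 0.59874 − 0.31512 = 0.0861. The plan gives less than 10%, which is right.

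**Step 2: evaluate each cut-off at both rates.**

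- P(X ≥ 1 | p = 0.05) = 1 − 0.95^10 = 0.4013.
- P(X ≥ 2 | p = 0.20) = 1 − 0.8^10 − 10(0.20)(0.8^9) = 1 − 0.10737 − 0.26844 = 0.6242.

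| Cut-off | True rate 20% | True rate 5% |
|---|---|---|
| At least 1 | 89.3% | 40.1% |
| 2 or more | 62.4% | 8.6% |
| 3 or more | 32.2% | 1.2% |

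No row has both about 90% on the left and under 10% on the right. The probabilities fall as the cut-off rises, so higher cut-offs do not help. For scale only, the smallest n with one cut-off reaching at least 90% at 20% and under 10% at 5% is 32 (4 or more: 90.7% and 7.4%).

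**Step 3: what N=10 delivers on the primary endpoint.** Apply the interval type Section 13 already plans, a two-sided 90% exact (Clopper-Pearson) interval, to the proportion of subjects with an SAE. The upper limit for x/10 solves P(X ≤ x | p) = 0.05. For x = 0 this is 1 − 0.05^(1/10) = 0.2589.

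| Observed | 90% exact interval |
|---|---|
| 0/10 | 0% to 25.9% |
| 1/10 | 0.5% to 39.4% |
| 2/10 | 3.7% to 50.7% |

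Even the most favourable result does not exclude the 20% rate used in the justification.

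**The case against.** Much of the case for the plan stands. Neither probability is a miscalculation: each names its own cut-off and reproduces at it, apart from 89.3% being given as 90%. They are offered as examples in a pilot that disclaims hypothesis testing and says its size is not power-based. The linking word can be read as introducing one illustration for a high rate and one for a low rate.

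A reader might therefore go too far and infer that the plan contains a safety rule with a 40.1% false-alarm rate, or one that misses a 20% rate 37.6% of the time (1 − 0.6242). The documents do not support this. They contain no such rule, and they never claim less than 10% for the one-SAE cut-off or 90% for the two-SAE cut-off. Nor do they tie a conclusion of good tolerability to any SAE count; Section 1.3 states tolerability as a hypothesis.

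Safety also has oversight: suspension after a possibly related death (Section 5.10), reporting of the frequency of adverse events of special interest (Section 7.1.4.1) and semi-annual toxicity reports (Section 11). None of these conveys the uncertainty in an SAE rate. It is also true that a descriptive analysis does not forbid an interval and that any reader could compute one from x/10. But the plan assigns its one interval to efficacy and still claims "this would provide us reasonable precision on both safety and feasibility". That claim is qualitative, with no target width, so it is better called unsupported than false.

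**Conclusion.** The point holds as one of presentation and reporting. The two stated probabilities are essentially right one at a time and misleading as a pair: the single-count figures are 89% against 40%, or 62% against 8.6%. The primary endpoint lacks the interval given to efficacy, and the 90% upper limits at N=10 (25.9%, 39.4% and 50.7% for 0, 1 and 2 subjects) do not support the claim of reasonable precision on safety.

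A reader might also infer that the study is too small or its design invalid. That does not follow: no decision depends on separating 5% from 20%, and the figure of 32 only shows the size of the gap. The results rest on the binomial assumptions listed in the working, chiefly that the SAE rate means the proportion of subjects with at least one SAE. This is a cheap improvement.

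**What to change.** Amend Section 13 in three places.

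1. Give both rates at the same cut-off, with 89% in place of 90%. For example: *With 10 subjects, the chance that at least one has an SAE is 89% if the true rate is 20% and 40% if it is 5%; the chance that two or more do is 62% and 8.6%.* Say that the rate is the proportion of subjects with at least one SAE.
2. Extend the planned 90% exact binomial interval to the proportion of subjects with at least one SAE and, optionally, with at least one adverse event of grade 3 or higher. Call it a descriptive measure, not a pass/fail criterion.
3. Replace the statement about precision on safety with the upper 90% limits: 25.9% for 0/10, 39.4% for 1/10 and 50.7% for 2/10.

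The cost is a few sentences and one or two intervals in the report. No patients or data are added: Section 7 already has events of grade 3 or higher recorded, and Section 7.1.4 already has SAEs reported to the supplier. The downside is a justification that looks less favourable.

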APPENDIX A. Clinical Differentiation of Acute and Chronic GvHD

Category	Time of Symptoms After alloHSCT or DLI	Presence of Acute GvHD Features	Presence of Chronic GvHD Features
Acute GvHD			
Classic acute GvHD	≤ 100 days	Yes	No
Persistent, recurrent, or late-onset acute GvHD	> 100 days	Yes	No
Chronic GvHD			
Classic chronic GvHD	No time limit	No	Yes
Overlap chronic GvHD	No time limit	Yes	Yes

DLI- donor lymphocyte infusion

APPENDIX B. Diagnostic Criteria for Chronic GvHD

Organ or Site	Diagnostic Features ¹	Distinctive Features ²	Others ³	Common Features ⁴
Skin	Poikiloderma Lichen planus-like features Sclerotic features Morphea-like features Lichen sclerosis-like features	Depigmentation Papulosquamous lesions	Sweat impairment Ichthyosis Keratosis pilaris Hypopigmentation Hyperpigmentation	Erythema Maculopapular rash Pruritus
Nails		Dystrophy Longitudinal ridging, splitting, or brittle features Onycholysis Pterygium unguis Nail loss		
Scalp and body hair		New onset of scarring or nonscarring scalp alopecia Loss of body hair Scaling	Thinning scalp hair, typically patchy, coarse, or dull Premature grey hair	
Mouth	Lichen-type features	Xerostomia Mucocoele Mucosal atrophy Pseudomembranes Ulcers		Gingivitis Mucositis Erythema Pain

Organ or Site	Diagnostic Features ¹	Distinctive Features ²	Others ³	Common Features ⁴
Eyes		New onset dry, gritty, or painful eyes Cicatricial conjunctivitis Keratoconjunctivitis sicca Confluent areas of punctate keratopathy	Photophobia Periorbital hyperpigmentation Blepharitis	
Genitalia	Lichen planus-like features Lichen sclerosis-like features	Erosions Fissures Ulcers		
Females	Vaginal scarring or clitoral/labial agglutination			
Males	Phimosis or urethral/meatus scarring or stenosis			
GI Tract	Esophageal web Strictures or stenosis in the upper to mid-third of the esophagus		Exocrine pancreatic insufficiency	Anorexia Nausea Vomiting Diarrhea Weight loss

Organ or Site	Diagnostic Features ¹	Distinctive Features ²	Others ³	Common Features ⁴
Lung	Bronchiolitis obliterans diagnosed with lung biopsy BOS ⁵	Air trapping and bronchiectasis on chest CT	Cryptogenic organizing pneumonia Restrictive lung disease ⁶	
Muscle, Fascia, joints	Fasciitis Joint stiffness or contractures secondary to sclerosis	Myositis or polymyositis ⁷	Edema Muscle cramps Arthralgia or arthritis	
Hematopoietic and immune			Thrombocytopenia Eosinophilia Lymphopenia Hypo- or hypergammaglobulinemia Autoantibodies (AIHA and ITP) Raynaud's phenomenon	
Other			Pericardial or pleural effusions Ascites Peripheral neuropathy Nephrotic syndrome Myasthenia gravis Cardiac conduction abnormality or cardiomyopathy	

1. Sufficient to establish the diagnosis of chronic GvHD
2. Seen in chronic GvHD, but insufficient alone to establish a diagnosis of chronic GvHD; In all cases, infection, drug effect, malignancy, or other causes must be excluded

3. Can be acknowledged as part of the chronic GvHD symptomatology if the diagnosis is confirmed
4. Shared features by both acute and chronic GvHD
5. BOS can be diagnostic for lung chronic GvHD only if distinctive sign or symptom present in another organ
6. Pulmonary entities under investigation or unclassified
7. Diagnosis of chronic GvHD requires biopsy

APPENDIX C. Performance Status Criteria

ECOG Performance Status Scale		Karnofsky Performance Scale	
Grade	Descriptions	Percent	Description
0	Normal activity. Fully active, able to carry on all pre-disease performance without restriction.	100	Normal, no complaints, no evidence of disease.
		90	Able to carry on normal activity; minor signs or symptoms of disease.
1	Symptoms, but ambulatory. Restricted in physically strenuous activity, but ambulatory and able to carry out work of a light or sedentary nature (e.g., light housework, office work).	80	Normal activity with effort; some signs or symptoms of disease.
		70	Cares for self, unable to carry on normal activity or to do active work.
2	In bed <50% of the time. Ambulatory and capable of all self-care, but unable to carry out any work activities. Up and about more than 50% of waking hours.	60	Requires occasional assistance, but is able to care for most of his/her needs.
		50	Requires considerable assistance and frequent medical care.
3	In bed >50% of the time. Capable of only limited self-care, confined to bed or chair more than 50% of waking hours.	40	Disabled, requires special care and assistance.
		30	Severely disabled, hospitalization indicated. Death not imminent.
4	100% bedridden. Completely disabled. Cannot carry on any self-care. Totally confined to bed or chair.	20	Very sick, hospitalization indicated. Death not imminent.
		10	Moribund, fatal processes progressing rapidly.
5	Dead.	0	Dead.

APPENDIX D. Organ Specific Staging of Chronic GvHD

	SCORE 0	SCORE 1	SCORE 2	SCORE 3
PERFORMANCE SCORE: 

 KPS ECOG LPS	 Asymptomatic and fully active (ECOG 0; KPS or LPS 100%)	 Symptomatic, fully ambulatory, restricted only in physically strenuous activity (ECOG 1, KPS or LPS 80-90%)	 Symptomatic, ambulatory, capable of self-care, >50% of waking hours out of bed (ECOG 2, KPS or LPS 60-70%)	 Symptomatic, limited self-care, >50% of waking hours in bed (ECOG 3-4, KPS or LPS <60%)
SKIN† 

 SCORE % BSA GVHD features to be scored by BSA: Check all that apply: 
  Maculopapular rash/erythema  Lichen planus-like features  Sclerotic features  Papulosquamous lesions or ichthyosis  Keratosis pilaris-like GVHD 	 No BSA involved	 1-18% BSA	 19-50% BSA	 >50% BSA
SKIN FEATURES SCORE:	 No sclerotic features	 Superficial sclerotic features "not hidebound" (able to pinch)	Check all that apply: 
  Deep sclerotic features  "Hidebound" (unable to pinch)  Impaired mobility  Ulceration 	
Other skin GVHD features (NOT scored by BSA) Check all that apply: 
  Hyperpigmentation  Hypopigmentation  Poikiloderma  Severe or generalized pruritus  Hair involvement  Nail involvement  Abnormality present but explained entirely by non-GVHD documented cause (specify): _____ 				
MOUTH Lichen planus-like features present:  Yes  No	 No symptoms	 Mild symptoms with disease signs but not limiting oral intake significantly	 Moderate symptoms with disease signs with partial limitation of oral intake	 Severe symptoms with disease signs on examination with major limitation of oral intake
 Abnormality present but explained entirely by non-GVHD documented cause (specify): _____				

	SCORE 0	SCORE 1	SCORE 2	SCORE 3
EYES	 No symptoms	 Mild dry eye symptoms not affecting ADL (requirement of lubricant eye drops ≤ 3 x per day)	 Moderate dry eye symptoms partially affecting ADL (requiring lubricant eye drops > 3 x per day or punctal plugs), WITHOUT new vision impairment due to KCS	 Severe dry eye symptoms significantly affecting ADL (special eyewear to relieve pain) OR unable to work because of ocular symptoms OR loss of vision due to KCS
Keratoconjunctivitis sicca (KCS) confirmed by ophthalmologist:  Yes  No  Not examined				
 Abnormality present but explained entirely by non-GVHD documented cause (specify):				
GI Tract	 No symptoms	 Symptoms without significant weight loss* ($<5\%$)	 Symptoms associated with mild to moderate weight loss* (5-15%) OR moderate diarrhea without significant interference with daily living	 Symptoms associated with significant weight loss* $>15\%$, requires nutritional supplement for most calorie needs OR esophageal dilation OR severe diarrhea with significant interference with daily living
Check all that apply:  Esophageal web/proximal stricture or ring  Dysphagia  Anorexia  Nausea  Vomiting  Diarrhea  Weight loss $\geq 5\%$  Failure to thrive				
 Abnormality present but explained entirely by non-GVHD documented cause (specify):				
LIVER	 Normal total bilirubin and ALT or AP < 3 x ULN	 Normal total bilirubin with ALT ≥ 3 to 5 x ULN or AP ≥ 3 x ULN	 Elevated total bilirubin but ≤ 3 mg/dL or ALT > 5 ULN	 Elevated total bilirubin > 3 mg/dL
 Abnormality present but explained entirely by non-GVHD documented cause (specify):				
LUNGS**				
Symptom score:	 No symptoms	 Mild symptoms (shortness of breath after climbing one flight of steps)	 Moderate symptoms (shortness of breath after walking on flat ground)	 Severe symptoms (shortness of breath at rest; requiring O_2)
Lung score:	 FEV1 $\geq 80\%$	 FEV1 60-79%	 FEV1 40-59%	 FEV1 $\leq 39\%$
% FEV1 				
Pulmonary function tests  Not performed				
 Abnormality present but explained entirely by non-GVHD documented cause (specify):				

	SCORE 0	SCORE 1	SCORE 2	SCORE 3
JOINTS AND FASCIA  No symptoms P-ROM score (see below) Shoulder (1-7): ____ Elbow (1-7): ____ Wrist/finger (1-7): ____ Ankle (1-4): ____	 Mild tightness of arms or legs, normal or mild decreased range of motion (ROM) AND not affecting ADL	 Tightness of arms or legs OR joint contractures, erythema thought due to fasciitis, moderate decrease ROM AND mild to moderate limitation of ADL	 Contractures WITH significant decrease of ROM AND significant limitation of ADL (unable to tie shoes, button shirts, dress self etc.)	
 Abnormality present but explained entirely by non-GVHD documented cause (specify): _____				
GENITAL TRACT (See Supplemental figure[†])  Not examined Currently sexually active  Yes  No	 No signs	 Mild signs [†] and females with or without discomfort on exam	 Moderate signs [†] and may have symptoms with discomfort on exam	 Severe signs [†] with or without symptoms
 Abnormality present but explained entirely by non-GVHD documented cause (specify): _____				
Other indicators, clinical features or complications related to chronic GVHD (check all that apply and assign a score to severity (0-3) based on functional impact where applicable none – 0, mild -1, moderate -2, severe – 3)				
 Ascites (serositis)____  Myasthenia Gravis____  Eosinophilia > 500/ μ l____				
 Pericardial Effusion____  Peripheral Neuropathy____  Platelets <100,000/ μ l ____				
 Pleural Effusion(s)____  Polymyositis____  Others (specify):_____				
 Nephrotic syndrome____  Weight loss>5%* without GI symptoms ____				
Overall GVHD Severity (Opinion of the evaluator)  No GVHD  Mild  Moderate  Severe				
Photographic Range of Motion (P-ROM)				

 
 Shoulder Elbow Wrist/finger Ankle 
 
 
 
				

APPENDIX E. Global Scoring of Chronic GvHD

Stage	Definition
Mild	1 or 2 organs involved with no more than score 1 plus Lung score 0
Moderate	At least 1 organ (not lung) with a score of 2 or 3 or more organs involved with no more than score 1 or Lung score 1
Severe	At least 1 organ with a score of 3 or Lung score of 2 or 3

In skin: higher of the 2 scores to be used for calculating global severity

In lung: FEV1 is used instead of clinical score for calculating global severity

If the entire abnormality in an organ is noted to be unequivocally explained by a non-cGVHD documented cause, that organ is not included for calculation of the global severity

If the abnormality in an organ is attributed to multifactorial causes (GVHD plus other causes) the score organ will be used for calculation of the global severity regardless of the contributing causes (no downgrading of organ severity score).

APPENDIX F. Minnesota-CIBMTR Staging and Grading for Acute GVHD

Acute GVHD Staging

	Stage 0	Stage 1	Stage 2	Stage 3	Stage 4
Skin (% BSA)	No rash	< 25%	25%-50%	> 50%	Generalized erythroderma with bullae
Gut (diarrhea, mL/day)	< 500	> 500	> 1000	> 1500	Severe abdominal pain +/- ileus
Upper GI		Persistent, severe nausea			
Liver (bilirubin, mg/dL)	≤ 2	2.1-3	3.1-6	6.1-15	> 15

BSA = body surface area; GI = gastrointestinal.

Acute GVHD Grading, MN-CIBMTR Criteria

Grade	Skin	Liver	Lower GI	Upper GI
Minnesota				
I	1-2	0	0	0
II	3	1	1	1
III	-	2-4	2-3	-
IV	4	-	4	-
CIBMTR				
A	1	0	0	0
B	2	1-2	1-2	1
C	3	3	3	-
D	4	4	4	-

APPENDIX G: Definitions for Adverse Event Reporting

A. Adverse Events (AEs)

As defined in 21 CFR 312.32:

Definition: any untoward medical occurrence associated with the use of a drug in humans, whether or not considered drug-related.

Grading: the descriptions and grading scales found in the revised NCI Common Terminology Criteria for Adverse Events (CTCAE) version 4.0 will be utilized for all toxicity reporting. A copy of the CTCAE version 4.0 can be downloaded from the CTEP website.

Attribution (relatedness), Expectedness, and Seriousness: the definitions for the terms listed that should be used are those provided by the Department of Health and Human Services' Office for Human Research Protections (OHRP). A copy of this guidance can be found on OHRP's website:

<http://www.hhs.gov/ohrp/policy/advevntguid.html>

B. Suspected Adverse Reaction (SAR)

As defined in 21 CFR 312.32:

Definition: any adverse event for which there is a reasonable possibility that the drug caused the adverse event. "Reasonable possibility" means there is evidence to suggest a causal relationship between the drug and the adverse event. "Suspected adverse reaction" implies a lesser degree of certainty about causality than adverse reaction, which means any adverse event caused by a drug.

C. Life-Threatening Adverse Event / Life Threatening Suspected Adverse Reaction

As defined in 21 CFR 312.32:

Definition: any adverse drug event or suspected adverse reaction is considered "life-threatening" if, in the view of the investigator, its occurrence places the patient at immediate risk of death. It does not include an adverse event or suspected adverse reaction that, had it occurred in a more severe form, might have caused death.

D. Serious Adverse Event (SAE) or Serious Suspected Adverse Reaction

As defined in 21 CFR 312.32:

Definition: an adverse event or suspected adverse reaction is considered "serious" if, in the view of the investigator, it results in any of the following outcomes:

- Death
- A life-threatening adverse event

- Inpatient hospitalization or prolongation of existing hospitalization
- A persistent or significant incapacity or substantial disruption of the ability to conduct normal life functions
- A congenital anomaly/birth defect
- Any other important medical event that does not fit the criteria above but, based upon appropriate medical judgment, may jeopardize the subject and may require medical or surgical intervention to prevent one of the outcomes listed above

E. Protocol Exceptions

Definition: A planned change in the conduct of the research for one participant.

F. Deviation

Definition: Any alteration or modification to the IRB-approved research without prospective IRB approval. The term “research” encompasses all IRB-approved materials and documents including the detailed protocol, IRB application, consent form, recruitment materials, questionnaires/data collection forms, and any other information relating to the research study.

A minor or administrative deviation is one that does not have the potential to negatively impact the rights, safety, or welfare of participants or others or the scientific validity of the study.

A major deviation is one that does have the potential to negatively impact the rights, safety, or welfare of participants or others or the scientific validity of the study.

